Official title:

**EFFECT OF A NUTRIGENETIC INTERVENTION ON BLOOD LIPID MARKERS AND BODY
COMPOSITION OF ADULTS WITH OVERWEIGHT AND OBESITY**

STUDY PROTOCOL

September, 30, 2021

“EFFECT OF A NUTRIGENETIC INTERVENTION ON BLOOD LIPID MARKERS AND BODY COMPOSITION IN OVERWEIGHT AND OBESO ADULTS”

STUDY PROTOCOL

- **Hypothesis**

A nutrigenetic diet administered to adults with genetic polymorphisms related to obesity and dyslipidemias will provide a greater decrease in plasma lipids, inflammatory markers and improvement in body composition, compared to the administration of a standard diet.

- **Objective:**

To evaluate the effect of a nutrigenetic intervention on blood biochemical and inflammatory markers and body composition in overweight and obese adults.

- **Design:**

Study type: Interventional

- **Interventional Study Model:**

Randomized controlled clinical trial, parallel assignment, with 2 study groups.

Two arms.

Masking: Single (participant).

Intervention period: 8 weeks.

Research site: ITESO and Centro Universitario de Ciencias de la Salud, Universidad de Guadalajara, México.

- **Methods:**

Participants

The recruitment of the population was carried out from the month of May to the month of September of the current year in the CD of Guadalajara, Jalisco and neighboring municipalities. The dissemination of informative flyers was done digitally through various social networks and also verbally.

Inclusion criteria

-Men and women

-18-50 years old

-Mexican- mexican ancestry (3 generations at least)

-Live in Guadalajara, Jalisco or metropolitan area

-Being overweight or obese (BMI 25>40)

-Waist circumference:

Women: > 80 cm

Men: > 94 cm

-Availability to attend virtual nutritional consultations.

Exclusion criteria

- Not meeting the inclusion criteria
- Pregnancy or breastfeeding
- Gastrointestinal disorders
- Endocrinopathies
- Cardiovascular events
- Diagnosed psychiatric illnesses
- Diagnosed diabetes
- Take lipid-lowering drugs
- Autoimmune diseases
- Covid +

Dependent variables:

Height, body weight, BMI, total body fat, fat mass index, skeletal muscle mass, visceral fat, waist circumference, hip circumference, total cholesterol (TC), LDL-cholesterol (LDL-C), HDL-cholesterol (HDL-C), triglycerides, C-reactive protein (CRP), glucose and insulin, total energy, macronutrients, micronutrients.

Independent variables:

Sex, age, presence or absence of polymorphisms, and intervention group.

INTERVENTION

All the subjects will give their written informed consent before inclusion in the study. The present study was approved by the ethical committee for human research of Instituto Tecnológico y de Estudios Superiores de Occidente (ITESO) (0001DRC) and was performed in accordance with the ethical standards laid down in the 1964 Declaration of Helsinki and its later amendments.

Randomization:

Participants will be randomly assigned, using a computerized random number generator (STATA software), to one of two treatments: nutrigenetic diet or conventional diet. Randomization will be stratified according to age, BMI and sex. The allocation ratio will be 1:1

Genotyping of gene polymorphisms related to dyslipidemias in Mexicans

Based on a previous systematic review, 11 gene polymorphisms associated with dyslipidemias in Mexicans were identified and were taken into account to perform genotyping in the study population.

The gene polymorphisms under study are:

ABCA1 rs9282541

PPARG rs1801282
LIPC rs1800588
CETP rs708272
LPL rs13702
FABP2 rs1799883
APOA5 rs662799
APOC3 rs5128
APOA1 rs670
APOE rs429358 and rs7412

A blood sample will be taken from the participants, then DNA will be extracted from leucocytes using a commercial extraction kit (High Pure PCR Template Preparation kit, *Roche*). Polymorphisms will be detected by a real-time RT-PCR system using allelic discrimination (TaqMan ®) in a 96-well format and will be read by a Roche LightCycler 96 system (Roche, Mannheim, Germany). PCR conditions will 40 cycles of amplification at 95°C for 10 min, and annealing/ extension at 60°C for 60 seconds.

The experimental phase will last 8 weeks.

Participants will attend 3 three visits to the clinical unit (Centro Universitario de Ciencias de la Salud, Universidad de Guadalajara): on the starting day of the intervention period (baseline), after 4 weeks (1st month) and after 8 weeks of intervention (final visit). Participants will also receive remote nutritional counseling every 15 days (5 consultations in total).

Anthropometric measurements

Anthropometric parameters will be measured three times during intervention period (baseline, week 4, week 8).

Measurements will be performed after 8- 10 hours of fasting. Height measurements will be taken using a stadiometer (Rochester Clinical Research, Rochester, NY, USA). Tetrapolar electrical bioimpedance will be used to assess weight and body composition (InBody 120 body composition analyser; Biospace, Seoul, Korea). BMI will be calculated as weight in kilograms divided by height in meters squared (kg/m²). The waist (narrowest diameter between the xiphoid process and the iliac crest) and hip (the widest diameter over the greater trochanters) circumferences will be measured (Lufkin anthropometric tape W606PM). Blood pressure will be measured, while seated, in the non- dominant arm using a digital automatic BP monitor (Model M3 Intelligence, Omron, Healthcare Company, Limited).

Biochemical measurements

Biochemical measurements will be performed three times during intervention period (baseline, week 4, week 8).

Venous blood samples will be taken after overnight fasting, and serum will be immediately separated by centrifugation. Measurements of total cholesterol, triglycerides, high-density lipoprotein cholesterol (HDL-C), glucose, very low density lipoprotein (VLDL) and C- reactive

protein will be performed using a Vitros-250 dry chemistry analyser (Ortho- Clinical Diagnostics, Johnson & Johnson Services, Inc., Rochester, NY, USA). LDL-C levels will be calculated using the Friedewald formula. The homeostatic model assessment of insulin resistance (HOMA-IR) will be calculated as described by Matthews et al. (1985). Insulin levels will be determined by an Immunoassay Kit (LIAISON®).

The inflammation markers IL-1, IL-6, IL-10 and TNF- α , will be determined using ProQuantum High-Sensitivity Immunoassays technique

Diets

As above-mentioned, patients will be randomly allocated to one of two diets for a period of 8 weeks.

NUTRIGENETIC DIET: Weekly, personalized meal plans (menus) will be provided every 2 weeks, prepared based on the anthropometric needs of the patients, with a caloric reduction (-500 kcal). These weekly menus (Sunday to Monday) consist of 5 meal times (breakfast, snack, lunch, snack and dinner). The distribution of the macronutrients: carbohydrates, proteins and fats, as well as the percentages of polyunsaturated, monounsaturated and saturated fatty acids, will be established according to certain nutrigenetic recommendations identified in the reference bibliography.

CONVENTIONAL DIET: weekly, personalized meal plans (menus) will be provided every 2 weeks, prepared based on the anthropometric needs of the patients, with a caloric reduction (-500 kcal). These weekly menus (Sunday to Monday) consist of 5 meal times (breakfast, snack, lunch, snack and dinner). The target macronutrient composition of this treatment is: 50% carbohydrates, 20% proteins and 30% fats in accordance with the recommendations made by the WHO (World Health Organization), the AHA (American heart association) and the NOM (Official Mexican Standards) for the treatment of obesity and dyslipidemias.

The percentages of macronutrients and fatty acids of all the menus will be adjusted using Foodprocessor nutrition software ®

All participants will receive remote (virtual) nutritional counseling every 15 days (5 individual sessions) with the dietitian to explain the diet, solve doubts, provide nutrition strategies and to complete the nutritional medical history, which includes physical activity record (IPAQ- short version) and questionnaires of frequency of food consumption to monitor adherence to nutritional intervention. Records will be analyzed with a computer-based data evaluation system (Foodprocessor nutrition software ®). National composition food tables will be also used as reference.

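### Only the participant is masked, although waist and hip are tape-measured outcomes that depend on the observer; whoever holds the tape, and the analyst, could be masked too

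*Protocol*

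**What the plan says.** The Interventional Study Model section of the protocol states "Masking: Single (participant". No other sentence in the protocol or SAP masks the outcome assessors or the analyst.

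The list of dependent variables includes "visceral fat, waist circumference, hip circumference, total cholesterol (TC" among many others. Under Anthropometric measurements, waist and hip "circumferences will be measured (Lufkin anthropometric tape W606PM"; the waist site is the narrowest point of the trunk between two bony landmarks. No repeat reading and no rule for tape tension is given. The timing is "Anthropometric parameters will be measured three times during intervention period (baseline, week 4, week 8".

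Measurement and diet delivery are described as separate contacts. For the first, "Participants will attend 3 three visits to the clinical unit". For the second, the Diets section says "All participants will receive remote (virtual) nutritional counseling every 15 days (5 individual sessions) with the dietitian". Neither document says which member of staff takes the measurements.

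Most other outcomes come from instruments. "Tetrapolar electrical bioimpedance will be used to assess weight and body composition", and blood pressure is read by an automatic monitor. Total cholesterol, which the SAP names as the primary outcome, is run on a chemistry analyser.

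**The concern.** Finding the narrowest point of the waist and setting the tape are matters of judgement. The hypothesis is directional: the nutrigenetic diet is expected to do better. A measurer who knows the arm and shares that expectation can shift readings by a small amount without intending to. A consistent shift by arm does not average out. It enters the between-arm difference directly, and a larger sample makes a false positive more likely.

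The analyst is a second route, and it reaches every outcome. The SAP lets the choice between parametric and non-parametric tests follow a distribution check, and it says that the mixed model will allow for confounders without naming them. Someone who can see which arm is which makes those choices with the result in view.

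At stake is the credibility of the waist and hip comparisons and, to a lesser degree, confidence that the analysis choices were neutral.

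**Working it through.** **Which outcomes are exposed**

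| Outcome | How it is obtained | Exposure to the measurer's knowledge of the arm |
|---|---|---|
| Total cholesterol (primary), other blood markers | Analyser or immunoassay; LDL-C by formula | Little |
| Weight, body composition | Bioimpedance device | Little |
| Blood pressure | Automatic monitor | Little |
| Waist, hip | Tape, site found by the observer | Yes |
| Energy and nutrient intake | Records taken in counselling with the dietitian | Not addressed by masking clinic-visit measurers |

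**Whether masking is feasible.** Counselling is virtual; anthropometry is done at three in-person visits. The tasks described for those visits are measurement and blood sampling, and neither requires the arm to be known. That makes masking possible in principle. It does not show that the measurer and the dietitian are different people.

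**How much a reading bias could matter.** The plan gives no figure for this, so the result is an illustration.

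From the documents:
- n = 24 per arm, the SAP's stated minimum. This reproduces from the SAP's effect size of 0.9772364 at 95% power with one-sided alpha 0.05: noncentrality 0.9772364 × √(24/2) = 3.385, critical t on 46 df = 1.679, power 95.4%. It is used here only as a sample size.
- n = 35 per arm: the recruitment target of 50 less the 30% loss, 50 × 0.70.

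Assumed, not in the documents:
- SD of waist change, σ: 3 to 4 cm.
- Systematic between-arm difference in reading, b: 0.5 or 1 cm.
- No true effect; two-sided 5% independent-samples t test.

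Formulas: noncentrality δ = (b/σ)√(n/2), with df = 2n − 2. With F the noncentral t distribution function and c the 97.5% point of the central t, the rejection probability is 1 − F(c; df, δ) + F(−c; df, δ). Here c = 2.013 for n = 24 (46 df) and 1.995 for n = 35 (68 df).

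| b (cm) | σ (cm) | b/σ | δ, n = 24 | Rejection, n = 24 | δ, n = 35 | Rejection, n = 35 |
|---|---|---|---|---|---|---|
| 0.5 | 4 | 0.125 | 0.433 | 7.1% | 0.523 | 8.1% |
| 0.5 | 3 | 0.167 | 0.577 | 8.7% | 0.697 | 10.6% |
| 1.0 | 4 | 0.250 | 0.866 | 13.6% | 1.046 | 17.8% |
| 1.0 | 3 | 0.333 | 1.155 | 20.4% | 1.394 | 28.0% |

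The nominal rate is 5%. Masking does not enter the sample-size calculation, so the plan's numbers per arm do not change.

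**The case against.** The strongest case against has five parts.

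- **The main conclusion is barely exposed.** The primary outcome is an analyser result, and the body composition in the title is read by bioimpedance. Waist and hip are two entries in a long list. This stands, and it confines the measurement part of the point to those two outcomes.
- **Staffing is unknown.** A reader might infer from the remote counselling that separate staff already do the measuring, so that masking would cost almost nothing. The documents name a place, not a person. The menus are prepared from the patients' anthropometric needs, so the dietitian uses these data and might collect them. The fix therefore has to be conditional.
- **Participants have little to reveal.** They are masked, and both arms receive personalised menus with the same energy reduction, meal pattern and counselling schedule. This limits leakage through participants. It does not help if the measurer can see the allocation list.
- **Analyst discretion is better cured by pre-specification, and coded arms are fragile.** Both parts are fair. Pre-specifying the tests and confounders is the direct remedy, and coding complements it. Dietary intake is an outcome, and the conventional arm has a fixed 50/20/30 macronutrient target, so intake data could show which code is which. They need to be kept apart.
- **Timing.** The protocol is dated 30 September 2021 and describes recruitment from May to September in the past tense. Whether anyone had been measured by then is not stated, so the change may be available only for later visits.

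**Conclusion.** The point holds as a modest improvement to a stated design choice. It is not an error or a contradiction. Participant-only masking leaves waist and hip open to observer bias and leaves the analyst's open choices unprotected, while the visit structure as described gives no reason for the measurer to know the arm.

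Its size depends on the assumed bias. At 0.5 cm the false-positive rate for waist is 7% to 11% across 24 to 35 per arm, not far above nominal; at 1 cm it is 14% to 28%. Neither the bias nor the SD comes from the documents, so no figure in this range is an estimate of what will happen.

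A reader might go further and conclude that the body-composition findings as a whole, or the cholesterol result, are compromised by unmasked measurement. The documents do not support that: those outcomes come from a device and an analyser, and only the analyst route touches them.

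**What to change.** State masking as participant, anthropometry assessor and analyst. In practice:

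1. Withhold the allocation list from whoever takes the tape measurements.
2. Ask participants not to discuss their menus at clinic visits.
3. Run the outcome models with arms coded A and B, and keep the dietary-intake data separate from the analyst until those outputs are final.
4. Leave the counselling dietitian unmasked, and say so.

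If participants have already been measured, apply this from the next visit on. If assessors were in fact masked, one sentence saying so settles that part.

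The cost is protocol wording, control of the allocation list and some data handling; sample size, visits and diets are unchanged. The downside arises if the counselling dietitian also takes the tape measurements: that task must then be reassigned within the existing team. If it cannot be, only the analyst part applies, and waist and hip should be reported as assessed unmasked.

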Official title:

**EFFECT OF A NUTRIGENETIC INTERVENTION ON BLOOD LIPID MARKERS AND BODY
COMPOSITION OF ADULTS WITH OVERWEIGHT AND OBESITY**

STATISTICAL ANALYSIS PLAN

September , 30, 2021.

Statistical analysis plan

Sample size was calculated *a priori*, considering the mean difference in total cholesterol between study groups as primary outcome variable (De Luis et al. 2017). GPower V3.1.9.4 software was used for the pertinent calculations. A power contemplated: 95%, and significance α : 0.5%. The effect size: 0.9772364. One-tailed, to analyze differences with the t-test. 30% loss to follow-up was considered. A minimum of 24 participants per treatment were required. The aim was to recruit 50 subjects per treatment

All the data will be analyzed using SPSS for MAC, version 26.0 software package (SPSS Inc. Chicago, IL). Parametric tests will be applied for quantitative variables with normal distribution, and non-parametric tests for qualitative and quantitative variables with abnormal distributions. The Kolmogorov–Smirnov test will be used to determine variable distribution. The results will be expressed as average \pm standard deviation.

For each treatment group, all markers will be tested using Student's paired-sample t test for possible difference between values achieved at baseline (visit 1) and 1st month (4 weeks) and visit 3 (final point, 8 weeks), respectively. Student's two independent- samples t tests will be also performed to find possible difference regarding these markers between treatments Nutrigenetic diet and Conventional diet. Furthermore, a mixed models approach including repeated-measures modeling will be utilized to find possible significant effects of the treatment effect at baseline on treatment effect after two subsequent clinical visits. This model will considerate confounders.

Categorical variables will be analyzed with the chi-square test, with Yates correction as necessary, and Fisher's test.

The statistical analysis to evaluate the gene-diet interaction was a univariate ANCOVA.

A Chi square test will be used to evaluate the Hardy–Weinberg equilibrium.

A P- value b 0.05 was considered significant.

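### The sample size paragraph prints an alpha of 0.5%, which conflicts with the SAP's 0.05 threshold and does not give its 24 per arm; one-tailed 5% gives exactly 24

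*SAP*

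**What the plan says.** The first paragraph of the SAP sizes the trial on the between-group mean difference in total cholesterol, the primary outcome, using G*Power. Its inputs are:

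- power and alpha: "A power contemplated: 95%, and significance α : 0.5", the last figure being followed by a percent sign;
- effect size: "The effect size: 0.9772364";
- test: "One-tailed, to analyze differences with the t-test";
- losses and result: "30% loss to follow-up was considered. A minimum of 24 participants per treatment were required".

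The paragraph then gives a recruitment aim of 50 per treatment. The Randomization section of the protocol sets 1:1 allocation.

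Two later statements in the SAP bear on alpha. The analysis paragraph plans independent-samples comparisons of the diets ("samples t tests will be also performed to find possible difference regarding these markers between treatments") without saying whether they are one- or two-sided. The last line reads "A P- value b 0.05 was considered significant", where the stray letter is evidently a misread less-than sign. It too is silent on sidedness.

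**The concern.** The SAP gives two significance levels a factor of ten apart, 0.5% for sizing and 0.05 for testing, with no reason for the difference. A stricter alpha needs a larger sample, so only one of them can be compatible with 24 per arm at 95% power.

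Alpha is a core input to the sample size for the primary outcome. A reader who takes the paragraph at face value finds a minimum that misses its stated power by about 20 percentage points, and a recruitment aim that also falls short of 95% after losses. A reader who assumes 5% finds a trial that is comfortably sized. The printed figure decides which impression is formed.

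Two gaps in the same text make checking harder. The planning test is one-tailed, but the sidedness of the actual test is not stated. And the sentence on 30% loss stands directly before the minimum of 24, so 24 can be read as already allowing for losses.

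**Working it through.** **Inputs.** Effect size d = 0.9772364, power 95%, one-tailed t-test, 30% loss, minimum 24 and aim 50 per arm (SAP, sample size paragraph); 1:1 allocation (protocol, Randomization). The effect size is read as a standardized mean difference, since no separate difference or SD is given.

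**Formula.** For two independent groups of n each:

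- degrees of freedom = 2n − 2
- noncentrality δ = d × √(n/2)
- one-tailed power = P(T > t₁₋α), where T is noncentral t with these two parameters
- two-sided power uses t₁₋α/₂ and adds the opposite tail.

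**Step 1: reproduce 24.** At n = 24, δ = 0.9772364 × √12 = 3.385 with 46 degrees of freedom.

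| One-tailed alpha | n per arm | Critical t | δ | Power |
|---|---|---|---|---|
| 0.05 | 23 | 1.680 | 3.314 | 94.71% |
| 0.05 | 24 | 1.679 | 3.385 | 95.45% |
| 0.005 | 24 | 2.687 | 3.385 | 75.39% |
| 0.005 | 39 | 2.642 | 4.315 | 94.997% |
| 0.005 | 40 | 2.640 | 4.370 | 95.55% |

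One-tailed 5% gives a minimum of exactly 24. One-tailed 0.5% gives 40; n = 39 falls just short, but neither is near 24.

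**Step 2: which alpha is compatible with 24?** Solving for the one-tailed alpha at which power is 95% gives 0.0458 at n = 24 and 0.0527 at n = 23. So 24 is the smallest sufficient n only for alpha from 0.0458 up to 0.0527. The printed 0.005 is about a tenth of that.

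**Step 3: other readings at 95% power.**

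- Two-sided 5%: n = 28 gives 94.85% and n = 29 gives 95.51%, so 29.
- Two-sided 0.5%: 44.
- Alpha taken as 0.5 without the percent sign: 6 one-tailed, 12 two-sided.
- 24 already including 30% loss: 24 × 0.7 = 16.8, about 17 evaluable. Power is 87.4% at one-tailed 5% and 55.0% at one-tailed 0.5%, so neither reaches 95%.
- Paired or one-sample t at one-tailed 0.5%: 23 in total. This is close by coincidence, but the SAP describes a between-group difference and a number per treatment.

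Of these readings, only one-tailed 5% with 24 before losses fits.

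**Step 4: losses and the aim of 50.** Dividing by 1 − 0.3 (an assumption, as the SAP does not state its convention), and taking 50 × 0.7 = 35 evaluable:

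| Test | n for 95% power | To recruit | Power at 24 | Power at 35 |
|---|---|---|---|---|
| One-tailed 5% | 24 | 24/0.7 = 34.3, so 35 | 95.4% | 99.2% |
| Two-sided 5% | 29 | 29/0.7 = 41.4, so 42 | 91.2% | 98.1% |
| One-tailed 0.5% | 40 | 40/0.7 = 57.1, so 58 | 75.4% | 92.1% |

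**The case against.** The strongest reply is that this is a self-evident slip. The only threshold the SAP applies to tests is 0.05, so no decision rule depends on the 0.5%. The planned 50 per arm gives ample power at 5%, and even if 0.5% were meant, 35 evaluable per arm would still give 92.1%. All of that is true and limits the consequence. It does not make the figure right: it is a wrong input to the primary outcome's sample size, and the calculation cannot be reproduced as printed.

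On sidedness, the sample size paragraph does name a one-tailed test, and the protocol's Hypothesis section is directional. That supports one-tailed planning. It does not say how the 0.05 will be applied in the analysis, so the two-sided figures above are conditional on a choice the SAP has not stated. This is an omission, not an arithmetic error.

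On losses, the separate aim of 50 already suggests that 24 is the number before losses, and the arithmetic agrees, so a clarification is enough. The 35 to recruit depends on the convention; multiplying by 1.3 instead gives 24 × 1.3 = 31.2, or 32. The aim of 50 covers either.

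Finally, 5% is inferred by back-calculation. The inference is strong, resting on two independent supports, but the saved G*Power output would settle it.

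**Conclusion.** The concern holds. The alpha of 0.5% is wrong as written: it contradicts the SAP's 0.05, and with the paragraph's other inputs it requires 40 per arm, leaving 24 per arm with 75.4% power against the stated 95%. One-tailed 5% reproduces 24 exactly. This rests on reading the effect size as Cohen's d for two independent, equal groups and on 24 being the number before losses.

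The trial is not shown to be underpowered. Under the evident 5% level the recruitment aim is sufficient for the stated effect size, whichever sidedness applies. The error must be corrected because the primary sample size rests on it, but the correction is to the document only.

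**What to change.** In the SAP:

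1. Check the saved G*Power output and change the alpha in the sample size paragraph from 0.5% to 5%, one-tailed.
2. State that 24 per treatment is the number before losses, and that 30% loss raises it to 35 to recruit, which the aim of 50 covers.
3. In the significance line, state whether the total cholesterol comparison at 0.05 is one- or two-sided. If two-sided, restate the justification as 24 per arm giving 91.2% power, or 29 per arm (42 to recruit) for 95%.
4. If 0.5% one-tailed was truly intended, correct the other figures instead: the minimum becomes 40 evaluable per arm (58 to recruit), the last line's 0.05 must change, and the aim of 50 would give 92.1% power after losses.

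Items 1 to 3 cost only wording, and enrolment need not change. Only item 4 would reopen the recruitment aim.

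### The SAP's minimum of 24 per treatment is the number before any loss to follow-up; with the 30% loss it should be 35, and the printed alpha of 0.5% does not give 24

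*SAP*

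**What the plan says.** The sample size paragraph of the SAP bases the calculation on total cholesterol, "considering the mean difference in total cholesterol between study groups as primary outcome variable". It gives "A power contemplated: 95%, and significance α : 0.5", with a percent sign after the 0.5, so alpha is printed as 0.005. It continues "The effect size: 0.9772364" and "One-tailed, to analyze differences with the t-test". Then come the loss and the result: "30% loss to follow-up was considered. A minimum of 24 participants per treatment were required". The paragraph ends "The aim was to recruit 50 subjects per treatment".

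Two other places bear on the calculation. The Protocol, under Randomization, says "The allocation ratio will be 1:1". The last line of the SAP sets the analysis threshold: "A P- value b 0.05 was considered significant" (the stray letter is most likely a less-than sign lost in text conversion and is not held against the plan).

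The SAP does not say whether 24 counts randomised participants or completers. It does not show how the 30% was applied or how 50 was reached. The Protocol contains no sample size.

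**The concern.** The sentence that mentions the loss comes directly before the minimum, so a reader will take 24 as the loss-adjusted figure. If it is not, the plan calls an enrolment sufficient that is expected to finish with too few completers.

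The stated minimum matters if recruitment misses the aim of 50. Any enrolment from 24 to 34 per arm would meet the minimum as written, yet 30% loss would leave fewer than 24 to analyse (34 × 0.70 = 23.8).

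The alpha printed in the same paragraph adds to the difficulty. It conflicts with the analysis threshold and, as shown below, with 24 itself, so the calculation cannot be checked from its stated inputs.

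**Working it through.** **Inputs.** Standardised effect d = 0.9772364, power 95%, one-tailed t-test and 30% loss (SAP, sample size paragraph); 1:1 allocation (Protocol, Randomization). The test is taken as two independent samples because the primary variable is a between-group difference. Two values of alpha appear: 0.005 (sample size paragraph) and 0.05 (last line of the SAP).

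**Formula.** With n evaluable per arm, degrees of freedom are 2n − 2, the noncentrality is d·√(n/2), and one-tailed power is P(T > t₁₋α), where T has the noncentral t distribution with those parameters.

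**1. Reproducing the plan's 24.** At one-tailed alpha 0.05:

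| n per arm | noncentrality | power |
|---|---|---|
| 23 | 0.9772364 × √11.5 = 3.314 | 94.7% |
| 24 | 0.9772364 × √12 = 3.385 | 95.4% |

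So 24 is exactly the smallest n reaching 95%, with no loss allowed for.

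**2. The printed alpha.** At one-tailed 0.005, 24 per arm has 75.4% power. Power is 94.997% at 39 and 95.6% at 40, so the requirement would be 40. With the stated d and power, 24 is the minimum only for a one-tailed alpha between 0.0458 and 0.0527. That range contains 0.05 and excludes 0.005.

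**3. Could 24 already contain the loss?** Then 24 × 0.70 = 16.8, so 16 or 17 evaluable per arm would have to give 95% power. At one-tailed 5% they give 85.5% and 87.4%. Reaching 95% would need either

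- a one-tailed alpha of 0.138 (n = 16) or 0.120 (n = 17), or
- d of 1.190 (n = 16) or 1.153 (n = 17).

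The SAP states none of these.

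**4. Loss-adjusted numbers.** Randomised per arm = evaluable ÷ (1 − 0.30). The aim of 50 leaves 50 × 0.70 = 35 evaluable.

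| One-tailed alpha | Evaluable per arm | Randomised per arm | Power with 35 evaluable |
|---|---|---|---|
| 0.05 | 24 | 24 / 0.70 = 34.3, so 35 | 99.2% |
| 0.005 | 40 | 40 / 0.70 = 57.1, so 58 | 92.1% |

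At one-tailed 5%, recruitment of 50 could lose 1 − 24/50 = 52% before falling below 24.

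**The case against.** The strongest reply is that 24 was never described as an enrolment figure. A number that is required is ordinary wording for what a power calculation returns. The next sentence gives recruitment separately as 50, and the loss sentence could belong to that figure. Read this way, 24 completers are needed, 50 are recruited to cover losses, and nothing is miscalculated; only a label is missing. Since 50 exceeds 35, the 30% is more than covered at one-tailed 5%. The scenario with 85% to 87% power requires stopping at 24 enrolled, contrary to the stated aim.

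Much of this stands. The completers reading is possible, and at one-tailed 5% the planned recruitment is ample. But even on that reading the loss-adjusted minimum is never given, 50 is not 24/0.70, and the text does not show what the 30% was used for. The printed alpha also remains in conflict with both 24 and the 0.05 threshold, so at least one stated figure is wrong however the 24 is read.

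Other settings do not rescue the paragraph. Two-sided 5% at 95% power needs 29 before loss. Two-sided 5% at 80% power needs 18, and multiplying by 1.3 gives 23.4, so 24; but that contradicts the stated tails and the stated power, and division by 0.70 would give 26. A paired calculation with the same d, one-tailed, gives 13 at 0.05 and 23 at 0.005 before loss, and would not match the between-group outcome.

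**Conclusion.** The concern holds. The figure of 24 per treatment contains no allowance for the 30% loss. As a number to randomise it is too low by 11 per arm (35 − 24). As a number of completers it is right but unlabelled, and the figure of 35 is missing.

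This rests on a one-tailed alpha of 5%. That is an inference, but a strong one: 24 reproduces there and not at the printed 0.5%, and the SAP's own significance threshold is 0.05. On that basis the planned trial is not underpowered, and what is wrong is the stated minimum and the alpha beside it. If 0.5% was meant literally, the conclusion is less comfortable: 24 is well short of 40, and the aim of 50 falls short of 58. The calculation also takes the effect size as given and assumes equal loss in the two arms.

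**What to change.** Restate the paragraph along these lines: 24 evaluable participants per treatment are required (one-tailed alpha 5%, 95% power, d = 0.977); allowing for 30% loss, at least 35 must be randomised per treatment; the recruitment aim of 50 leaves about 35 evaluable. Correct the printed alpha to the value actually used in the calculation.

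If 0.5% was intended, replace 24 and 35 with 40 and 58, state that recruiting 50 per treatment gives about 92% power after 30% loss, and reconcile that alpha with the 0.05 threshold in the last line.

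At one-tailed 5% the cost is SAP wording only: the aim of 50 already exceeds 35, so neither design nor analysis changes. At 0.5%, keeping 95% power would take 8 more recruits per arm (58 − 50); otherwise the lower power has to be accepted and stated.
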